6.3.3 Medical History

Medical Histories will be summarized for the ITT by Treatment Sequence and overall by using system organ class (SOC) and preferred term (PT) with frequencies and proportions of subjects that experienced each level. Medical Histories will be provided in a data listing.

6.3.4 Exposure and Adherence

The proportion of subjects who permanently discontinued blinded investigational drug, overall and by reasons for discontinuation, will be summarized overall and by Treatment Group within Randomized Sequence.

The proportion of subjects who experienced at least one temporary holding of blinded investigational drug, overall and by reasons for holding, will be summarized by treatment arm. Descriptive statistics of the duration of exposure to investigational drug in total and adjusted for temporary holds will be summarized by the treatment arm. Treatment duration, calculated as the number of days the subject received randomized investigational drug will be calculated as the date of the last dose minus the date of the first randomized dose + 1. The duration will be adjusted for temporary holds by subtracting days the investigational drug was temporarily held.

Treatment adherence will be defined by the treatment adherence ratio: the number of doses taken by the subject divided by the number of doses assigned.

Adjusted treatment adherence will be defined by the treatment adherence ratio: the number of doses taken by the subject divided by the number of doses assigned adjusting for the treatment holds.

A listing of the exposure and adherence parameters will be provided, including reasons for modification, if they occur.

6.3.5 Prescribed AHT

A listing of each patient prescribed AHT therapy will be provided.

6.4 Efficacy Evaluation

All efficacy analyses will be performed using the FAS unless stated otherwise.

The efficacy analyses of primary and exploratory endpoints will provide the observed values at each Baseline (TP1 baseline and TP2 baseline), the end of each treatment period (TP1 Treatment Week 4 and TP2 Treatment Week 4), and the change from baseline by each treatment arm in addition to model estimates.

Analyses including repeated visits / time points will include each repeated visit/time point considered in the model. Parameter estimates that include multiple repeated visits / time points may be presented if specified for analysis.

A summary table of each assessment will provide the observed value and change from baseline for each scheduled visit by Randomized Sequence and treatment period and totals by treatment group, unless otherwise specified.

Line plots of blood pressure mean value over time and change from baseline over time with 95% CIs will be provided by treatment arm and treatment period. Endpoints estimated with analysis models will also plot LS Means and their 95% CIs for each time point.

Box-and-whiskers plots of observed data distributions will be provided for primary endpoint for treatment arm and treatment period. A box-and-whiskers for model analysis estimates of LS Means will plot Standard Error of the Mean (instead of Q1/Q3) and 95% CIs (instead of Min/Max). A waterfall plot of the change in systolic blood pressure will be provided overall and separately for treatment period.

Categorical analysis will display the number and proportion of patients that meet the endpoint at baseline and for the time point of interest. Proportions at the endpoint's time point will only consider those that did not meet criteria at baseline.

Categorical endpoints will be presented with Bar Charts of proportion and 95% CIs.

6.4.1 Primary Efficacy Endpoint Analysis

Endpoint: Placebo-adjusted change in AOBP SBP from TP baseline to TP Week 4

6.4.1.1 Estimand Question

The Primary Efficacy Endpoint estimand is designed to answer the question of the effect of lorundrostat in a dose of 25 mg QD for 4 weeks on blood pressure in subjects with uncontrolled hypertension and CKD with albuminuria on treatment with SGLT2i and a prescribed AHT medication regimen including ACEi or an ARB.

6.4.1.2 Estimand Definition

This estimand is constructed in line with ICH E9 (R1) addendum and described below.

Table 4 Definition of the estimand for the primary efficacy endpoint

Population:	Patients aged 18 years and older with a history of medically treated hypertension and CKD with albuminuria whose blood pressure prior to initiation of study treatment is uncontrolled based on blood pressure measured by AOBP despite being prescribed antihypertensive therapy including a stable dose of ACEi or ARB. In addition, subjects are on a treatment with SGLT2i. Additional inclusion and exclusion criteria as specified in protocol apply. Only patients who receive at least one dose of the study treatment (lorundrostat or placebo) are included.
-------------	--

Treatment	Treatment is lorundrostat 25 mg QD for 4 weeks on a background of the prescribed AHT medication regimen including a stable dose of ACEi or ARB and SGLT2i. The treatment is administered in the cross-over randomized sequence (Lorundrostat/Placebo or Placebo/Lorundrostat) with a 4-week washout in between.
Variable	AOBP SBP at Treatment Week 4 (TP1 Week 4 and TP2 Week 4)
Population-level summary	Mean placebo-adjusted change in AOBP SBP from Treatment Period baseline to Treatment Period Week 4
Handling of ICE events	Is described in the Table 5.

Table 5 Handling of ICE for the primary efficacy estimand

ID	Description of ICE	Type of the Event	Observations handling (Strategy)	Rationale
1	Permanent discontinuation ¹ of investigational drug (lorundrostat or placebo) due to adverse events, clinically significant laboratory finding or due to medical assessment as described in the protocol	Treatment-modifying event	Treatment Policy Strategy: Observations for subjects with ICE will be used regardless of occurrence of ICE	Permanent discontinuation of the investigational treatment due to AEs, significant laboratory findings and protocol defined medical assessments are anticipated to occur in the clinical practice and the estimate of the treatment effect of intervention needs to incorporate these events.

¹ Temporary discontinuation (“drug holds”) or dose modification do not qualify as ICE. Modification or changes in background prescribed AHT medications do not qualify as ICE.

ID	Description of ICE	Type of the Event	Observations handling (Strategy)	Rationale
2	Death for any cause	Censoring Event	Composite Strategy: The endpoint will be imputed to assign a poor outcome value by applying a distribution of the worst 5% of the observations across all arms	The treatment policy strategy is not applicable as there are no post-event observations.

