7. DISCONTINUATION / WITHDRAWAL CRITERIA

7.1 Discontinuation of Study Drug

Subjects who wish to stop treatment for any reason may stop at any time during the study.

Reasons for discontinuing study drug may include:

- Unavoidable use of prohibited/excluded medications (see [Section 6.9](#))
- Administrative decision by the Investigator or the Sponsor
- Chronic or repeated subject noncompliance with the study drug dosing schedule (see [Section 6.5](#))
- Development of an AEs/SAEs/AESI at the discretion of the site Investigator, in consultation with the Medical Monitor. If the site Investigator deems the event urgent, then study drug should be held and consultation with the Medical Monitor regarding potential restart of study medication at the assigned or a reduced dose should be performed (see [Section 6.7](#))
- Unblinding of subject's study drug treatment assignment (see [Section 6.4](#))
- Subject becomes pregnant or wishes to discontinue birth control measures (see [Section 8.4.5](#))
- Any other reason that, in the opinion of the Investigator, precludes the subject's further participation in the trial

Subjects who permanently discontinue study drug will continue participation in the study, including participation in all remaining visits and assessments until the EoS visit. Subjects who have permanently discontinued study drug will not progress to the OLE study.

Details regarding subjects who discontinue study drug will be recorded on the appropriate page(s) of the eCRF. If a subject discontinues study drug because of an AE, the Investigator may be requested to schedule follow-up visits until the event has resolved or stabilized ([Section 4.6](#)).

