6 STATISTICAL METHODS

6.1 Sample Size Justification

Approximately 60 subjects randomized in a 1:1 ratio to the two sequences (LP and PL) will provide 85% power to detect a placebo-adjusted change in AOBP SBP of at least 5.5 mmHg at Treatment Period Week 4 (pooling both Treatment Periods in a joint longitudinal analysis), assuming 14 mmHg as a standard deviation of change, and 1-sided alpha of 0.05.

Power for a joint analysis is a function of the alternative (assumed 5.5 mmHg), the standard deviation (assumed 14 mmHg), and both the within-treatment-period correlation denoted ρ_1 , and the between-treatment-period correlation denoted ρ_2 . We consider a simple exchangeable correlation model where $\rho_2 = \rho_1$, and a time decay model where $\rho_2 = \rho_1^2$. The following table shows power as a function of the correlation model using analytical expressions for standard errors obtained from the primary linear mixed model analysis:

Correlation (ρ_1)	Power assuming Exchangeable model ($\rho_2 = \rho_1$)	Power assuming Time decay model ($\rho_2 = \rho_1^2$)
0.50	0.819	0.756
0.55	0.850	0.785
0.60	0.882	0.819
0.65	0.915	0.858
0.70	0.945	0.900
0.75	0.971	0.941
0.80	0.988	0.975

Crossover trials generally find a correlation model that closely approximates an exchangeable model since this corresponds to a common magnitude of between subject variation that would be induced from a simple random intercepts model (see Jemielita, Putt and Mehrotra 2016 for examples). Under the exchangeable correlation model, the study has $\geq 85\%$ power provided the correlation is ≥ 0.55 .

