6.2.4 Alpha Value

The overall alpha (α) value is set to one-sided 0.05. The primary and all exploratory endpoints will be tested on the same one-sided alpha of 0.05. The confidence intervals for all analyses will be 90%.

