6.4.1.3 Missing Observations for the AOBP SBP

For general guidance about the missing values, see 6.2.7. Guidance on handling the missing observations is provided below.

Table 6 Missing observations imputation for the primary efficacy estimand

Cause for Missing Observation	Type of Missingness	Imputation Approach	Rationale
Lack of follow-up observation in subject with ICE ID #1.	MNAR	Values for the missing observation will be imputed using the distribution for the subjects with ICE ID#1 who do not miss the value (so called “retrieved dropouts”), within the same randomized sequence, if such approach is possible. In case there are not enough retrieved dropouts within the same sequence, the imputation will be performed by Jump to the Reference Group (Placebo Arm)	Retrieved dropouts’ imputation is closest to following a treatment strategy for missing observations. Jump to reference as a last resort is conservative imputation strategy that disfavors treatment effect.
Death for any cause (ICE Event #2)	MNAR	This observation is missing by default. The endpoint will be imputed to assign a poor outcome value by applying a distribution of the worst 5% of the observations across both randomized sequences.	The treatment policy strategy is not applicable as there are no post-event observations. Death, as an unfavorable truncating event prevents observations to be obtained.
Premature study discontinuation in subjects without ICE (e.g. loss to follow-up, withdrawal of consent)	MAR	Values for the missing observations will be imputed using the randomized sequence specific distribution	These observations are assumed to be missing at random and will be imputed as a part of the treatment arm they belong to.

Cause for Missing Observation	Type of Missingness	Imputation Approach	Rationale
Missing observation due to failure to obtain AOBP in subjects without ICE	MAR	Values for the missing observations will be imputed using the randomized sequence specific distribution	AOBP may fail for technical reasons or subject may miss the visit. These observations are assumed to be missing at random and will be imputed as a part of the treatment arm they belong to.

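### Permanent drug stops for reasons other than an AE, laboratory or medical finding have no intercurrent-event strategy, and a missing Week 4 value after one is imputed under MAR from a mostly on-drug pool

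*SAP*

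**What the plan says.** SAP 6.4.1.2, Table 5, names two intercurrent events. One is death. The other (ICE #1) is permanent discontinuation of lorundrostat or placebo "due to adverse events, clinically significant laboratory finding or due to medical assessment as described in the protocol", handled by treatment policy. A footnote excludes drug holds, dose changes and background antihypertensive changes. It does not mention permanent stops for other reasons.

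Protocol 7.1 is wider: "Subjects who wish to stop treatment for any reason may stop at any time during the study". Its list also includes prohibited medication, administrative decision, noncompliance, unblinding, pregnancy or ending contraception, and investigator opinion. It keeps subjects who stop drug in the study for their remaining visits.

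SAP 6.4.1.3, Table 6, sets the imputation. A Week 4 value missing after ICE #1 is MNAR: it is imputed from retrieved dropouts in the same sequence or, if these are too few, by jump to placebo. The row that begins "Premature study discontinuation in subjects without ICE (e.g. loss to follow-up, withdrawal of consent" is MAR, as is the row for a failed or missed AOBP in a subject without an ICE. Both draw from the distribution for the randomized sequence, and the rationale column says the subject is imputed as a member of the assigned arm.

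**The concern.** A subject who has permanently stopped drug is off drug whatever reason is recorded. Under Table 6 the reason decides the imputation: retrieved dropouts or placebo after an AE stop, but the general sequence distribution after, say, a stop by the subject's wish. Most of that distribution comes from subjects still taking drug.

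The protocol describes a short half-life (2.1, 2.2) and a blood pressure effect that available data suggest is reversible (4.2). Imputing an off-drug lorundrostat value largely as treated would therefore tend to enlarge the estimated effect relative to treatment policy. The crossover adds a second route: a PL subject who stops in Period 1 for an unlisted reason and misses Week 12 could be imputed as a lorundrostat observation without having taken the drug.

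**Working it through.** **1. The four routes for a subject permanently off drug**

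| Recorded reason | Week 4 measured | Week 4 missing |
|---|---|---|
| AE, laboratory, medical | Kept (treatment policy, Table 5) | Retrieved dropouts, else jump to placebo |
| Any other | Kept (no SAP rule removes it) | MAR from the sequence distribution |

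The rows differ only in the last column. In the second row, attenders and non-attenders are handled on different principles.

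**2. The scale for comparison**

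SAP 6.1 states "Approximately 60 subjects randomized in a 1:1 ratio to the two sequences (LP and PL) will provide 85% power" for a "placebo-adjusted change in AOBP SBP of at least 5.5 mmHg at Treatment Period Week 4", "assuming 14 mmHg as a standard deviation of change, and 1-sided alpha of 0.05". The SE that gives 85% power is

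SE = 5.5 / (z0.95 + z0.85) = 5.5 / (1.645 + 1.036) = 2.05 mmHg.

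I could not reproduce the SAP's 0.850 at an exchangeable correlation of 0.55 from the printed inputs. With power = Φ(5.5/SE − 1.645) and N = 60:

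- Period difference adjusted for baseline difference: SE = √(2 × 14² × 0.45 / 60) = 1.71, power 0.941.
- Difference of change scores: SE = √(4 × 14² × 0.45 / 60) = 2.42, power 0.733.
- ANCOVA on own-period baseline: power 0.878.
- Model with a persistent carryover term: power 0.783.
- 14 mmHg taken as the SD of the within-subject difference: power 0.919.

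The SAP does not print the analytical expressions it used, so this is not evidence of an error. The mmHg figures below do not depend on it. Only the SE multiples do.

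**3. The overstatement**

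Let q be the share of subjects who stop for a non-ICE reason and also lack the lorundrostat-period Week 4 value. Let m be the mean effect in the imputation pool and d the effect remaining off drug. Then

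overstatement relative to treatment policy = q × (m − d).

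With a true on-drug effect of 5.5 mmHg, m cannot exceed 5.5, and taking d = 0 gives the bound q × 5.5. The documents give no value for q, so a range is assumed.

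| q (of 60) | Treatment-policy effect, (1 − q) × 5.5 | Overstatement, q × 5.5 | Divided by 2.05 |
|---|---|---|---|
| 5% (3) | 5.23 | 0.28 | 0.13 |
| 10% (6) | 4.95 | 0.55 | 0.27 |
| 15% (9) | 4.68 | 0.83 | 0.40 |

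A mixed pool lowers the figure. If a tenth of the observed values in the pool were themselves off drug, m = 0.9 × 5.5 = 4.95, and at q = 10% the overstatement is 0.10 × 4.95 = 0.50 instead of 0.55.

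**4. Simulation check of the algebra**

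The 2×2 crossover was simulated with 2,000 trials per share, a baseline-difference-adjusted model and imputation within sequence, under the same bounding assumptions.

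| q | Treatment-policy truth | MAR imputation | Jump to reference |
|---|---|---|---|
| 5% | 5.23 | 5.51 | 5.23 |
| 10% | 4.95 | 5.52 | 4.96 |
| 20% | 4.46 | 5.50 | 4.46 |

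With no drug effect and q = 10%, MAR gave 0.06 mmHg and treatment policy 0.05. The simulation confirms the formula; it says nothing about what q will be.

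**5. Would the sensitivity analyses show it?**

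SAP 6.4.1.5 lists, in its readable text, observed data only, all missing values MAR, and a longitudinal linear model. The first two are no more conservative than the primary rule for these subjects. The missing-data assumption of the third is not stated. No reference-based or tipping-point analysis appears.

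**The case against.** The strongest reply has five parts.

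- **The group is narrow.** Protocol 7.1 keeps subjects in follow-up after stopping, SAP 2.5 says the same after unblinding, and SAP 5.5.1 maps early-withdrawal assessments to analysis visits and can use an earlier measurement. This stands, and 15% may be far too high for the joint event.
- **The pool is a mixture.** It contains observed off-drug values, and Table 6 does not say whether it is period-specific; the on-lorundrostat reading rests on the rationale column. This also stands, so q × 5.5 is an upper bound.
- **The ICE boundary is not sharp.** The protocol's dose-modification text gives medical assessments as an open list of examples, so pregnancy or prohibited medication might arguably fall inside ICE #1. The subject's wish, administrative decisions, noncompliance and unblinding are harder to place there.
- **Splitting discontinuations by reason is legitimate.** A hypothetical strategy for trial artefacts such as unblinding would fit MAR. This is true in principle, but the SAP declares no such strategy and removes no observed off-drug values after these stops. Attenders are therefore under treatment policy in practice while comparable non-attenders are imputed as mostly on drug. A hypothetical strategy does not describe that combination.
- **No false positive arises from this mechanism.** The null simulation agrees.

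A reader might infer that affected subjects are credited with the drug's full effect, that the two imputations are opposites, or that the SAP contradicts a treatment-policy aim it has declared. The documents do not support this. The pool is mixed, jump to placebo is only the fallback after retrieved dropouts, and treatment policy is declared for ICE #1 alone.

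**Conclusion.** The gap is real and lies in the stated rules, not only in missing detail. Permanent stops that Protocol 7.1 foresees have no estimand strategy, and Table 6 imputes the same off-drug state differently according to the recorded reason, in a direction that tends to favour lorundrostat.

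The size is modest and uncertain. The bound of 0.28 to 0.83 mmHg on 5.5 mmHg rests on four assumptions: an affected share of 5% to 15%, a fully on-drug pool, no effect left after stopping, and treatment policy as the target. A smaller share, a mixed pool or a residual effect makes it smaller. The documents do not establish that the primary estimate will be materially biased. They leave the question open and list no analysis in the readable text that is clearly able to answer it. This should be corrected before unblinding, but it does not threaten the test under the null.

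**What to change.** - **Table 5:** define ICE #1 as permanent discontinuation of investigational drug for any reason, with treatment policy.
- **Table 6:** apply the ICE #1 imputation (retrieved dropouts, else jump to placebo) to every such subject with a missing Week 4 value. Keep MAR for subjects still taking that period's study drug at last contact.
- **Section 6.4.1.5:** add a reference-based sensitivity analysis that also covers subjects who left before receiving any lorundrostat. A PL subject lost during Period 1 while still taking placebo is not caught by the ICE wording alone.
- If the sponsor prefers a hypothetical strategy for particular reasons, the SAP should name them, justify the choice, and handle observed post-stop values to match.

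The cost is SAP wording and a little programming, with no change to data collection. The estimate may be slightly smaller. With the SE held at 2.05 mmHg, power at the treatment-policy effect would be 81.7%, 77.9% or 73.7% for assumed shares of 5%, 10% or 15%.

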4.1.4 Full Analysis Set (FAS)

The Full Analysis Set (FAS) will include all randomized subjects who receive at least one dose of investigational study drug (lorundrostat or placebo). Subjects will be categorized according to the treatment assignment. Efficacy outcomes will be analyzed using the FAS, unless otherwise specified.

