First investigational drug administration during TP1 will be selected from the “Investigational Drug Administration” CRF page for the Randomization Visit or vendor AiCure’s Dosing Diary data (selecting the first [Lorundrostat or Placebo] record following randomization) – the earlier available from each source.

Last investigational drug administration during TP1 will be selected from the “Investigational Drug Administration” CRF page for the Study Week 4 visit if the drug was administered at the Week 4 visit or, vendor AiCure’s Dosing Diary data (selecting the last [Lorundrostat or Placebo] record on or prior to Week 4 Study Visit Date, the latest available from each source.

First investigational drug administration during the Washout Period will be selected for the subjects who were dispensed placebo after the TP1 from the vendor AiCure’s Dosing Diary data (selecting the first [Placebo] record following Week 4 Visit. If that is not available, the first dose will be imputed as Week 4 Visit Date +1 day at 08:00 AM if the subject was dispensed placebo.

First investigational drug administration during TP2 will be selected from the “Investigational Drug Administration” CRF page for Study Week 8 visit if the administration occurred on Week 8 visit date or, vendor AiCure’s Dosing Diary data (selecting the first [Lorundrostat or Placebo] record on or after Week 8 visit [“Investigational Drug Administration” or “Date of Visit” CRF pages]) – the earlier available from each source. Only subjects who were dispensed drug on Week 8 visit record can have this information.

Last investigational drug administration during TP2. Only subjects with the First investigational dose administration in TP1 may have the last investigational drug administration in TP2. The last administration will be selected from the “Investigational Drug Administration” CRF page for Week12 / EoT visit (when study drug was administered at the visit) or vendor AiCure’s Dosing Diary data (selecting the last [Lorundrostat or Placebo] record following Week 12 visit [“Investigational Drug Administration” or “Date of Visit” CRF pages]) – the latest available from each source.

Safety Follow-up Period: All observations and measurements following End of Treatment Period 2 are considered safety Follow-up Period, including the EoS (Week 14/EoS) visit.

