6.4.1.4 Primary Efficacy Estimation

The primary analysis of the primary efficacy estimand will assess the superiority of lorundrostat 25 mg QD dose compared to placebo in mean change in AOBP SBP from TP baseline (TP1 Baseline and TP2 Baseline) to TP Week 4 (TP1 Week 4 and TP2 Week4).

The analysis includes two baselines (TP1 baseline and TP2 baseline). The primary analysis will be based on the work of Mehrotra DV, 2014 and Jemielita, T., et al. 2016. Specifically, the Model IV from Mehrotra DV, 2014 will be used for the primary analysis as the best performing model for pairwise correlation of 0.6 and balanced 2x2 design. Sensitivity analyses will use additional models as specified later.

Example of SAS code for the planned estimation is provided below. The actual code may differ from the example depending on the data, carry-over effect and convergence.

```
proc mixed data = file;  
class trtseqp aperiodc trtp usubjid;  
model aval = xdiff trtseqp aperiodc xdiff*aperiodc trtp ;  
repeated aperiodc/subject=usubjid(trtseqp) type=un;  
estimate 'Lorundrostat v placebo' trtp 1 -1 /cl alpha=0.1;  
lsmeans trtp /pdiff cl alpha=0.1;
```

where,
trtseqp is a planned treatment sequence (Lorundrostat-Placebo and Placebo-Lorundrostat),
aperiodc is analysis period (TP1 and TP2),
trtp is planned treatment (Lorundrostat and Placebo),
xdiff is a difference between TP1 baseline and TP2 baseline.

The estimate statement depends upon the coding of the variables and needs to be adjusted accordingly.

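### ICE 1 should cover permanent discontinuation for any reason and be recorded by treatment period, with a sensitivity analysis for placebo-first subjects never dosed in Period 2

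*SAP*

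**What the plan says.** SAP Table 5 (section 6.4.1.2) defines ICE 1 as permanent discontinuation "of investigational drug (lorundrostat or placebo) due to adverse events, clinically significant laboratory finding or due to medical assessment as described in the protocol". The strategy is treatment policy: "Observations for subjects with ICE will be used regardless of occurrence of ICE". Neither the row nor its footnote says in which treatment period, or on which product, the stop occurs. The rationale is that such stops happen in practice and belong in the effect of the intervention.

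Protocol 7.1 gives a longer list of reasons for stopping. It includes unavoidable prohibited medication, administrative decision, repeated noncompliance and unblinding. Whatever the reason, "Subjects who permanently discontinue study drug will continue participation in the study, including participation in all remaining visits and assessments until the EoS visit".

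SAP Table 6 (section 6.4.1.3) treats a missing value after ICE 1 as MNAR. It is imputed from retrieved dropouts of the same sequence or, failing that, by jump to reference. A missing value in a subject with no ICE is treated as MAR: "Values for the missing observations will be imputed using the randomized sequence specific distribution".

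On classification, the estimand population is met by a single dose of either product: "Only patients who receive at least one dose of the study treatment (lorundrostat or placebo) are included". For the FAS, "Subjects will be categorized according to the treatment assignment". The legend to the model code in SAP 6.4.1.4 reads "trtp is planned treatment (Lorundrostat and Placebo". SAP 5.2, on deriving the first Period 2 dose, notes: "Only subjects who were dispensed drug on Week 8 visit record can have this information". The plan therefore foresees subjects with no Period 2 dose.

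**The concern.** (a) Reason for stopping. Two subjects who are both permanently off drug and both lack a Week 4 reading are imputed differently according to why they stopped. The adverse-event stopper gets an off-drug or placebo-like value. The subject stopped for unblinding or noncompliance gets a value from a sequence whose members are mostly on drug at that visit. A treatment-policy estimand asks what happens after stopping, whatever the reason, so the split does not fit the plan's own strategy. In lorundrostat periods it leans towards the drug.

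(b) Period. A placebo-first (PL) subject who permanently stops during Period 1 or the placebo washout still attends Weeks 8 and 12. The Week 12 value enters as a lorundrostat outcome, although no lorundrostat was taken. The Table 5 rationale concerns stopping the intervention because of how it is tolerated. It does not describe an event on placebo that keeps the intervention from starting, which arises only from the order of a crossover. This leans towards no effect.

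**Working it through.** **Tracing the rules**

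| Subject | Week 4 value of the period | Rule that applies |
|---|---|---|
| Stops for AE, laboratory or medical reason | observed | used (Table 5, ICE 1) |
| Same | missing | MNAR: retrieved dropouts, else jump to reference (Table 6) |
| Stops for another Protocol 7.1 reason | observed | no strategy in Table 5, but no rule excludes it |
| Same | missing | no ICE, so MAR from the sequence distribution (Table 6) |
| PL, ICE 1 in Period 1 or washout | Week 12 observed | used, labelled lorundrostat by planned treatment |

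Row four against row two is gap (a). Row five is gap (b).

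**The plan's own figure.** The inputs are about 60 subjects (30 per sequence), a 5.5 mmHg difference, SD 14 mmHg and one-sided alpha 0.05, with stated power 85% (Protocol 9.5, SAP 6.1).
- Taking 14 as the SD of the within-subject difference, 5.5/(14/√60) = 3.04. The normal approximation then gives power 0.919 at one-sided 0.05 and 0.861 at two-sided 0.05. The 85% is close to the two-sided calculation, not the stated one-sided one.
- The SAP table entry of 0.850 at correlation 0.55 (exchangeable) was not reproduced by the model variants tried.
- Power below is therefore anchored on the stated 85%. The implied standard error is 5.5/(1.645 + 1.036) = 2.05 mmHg.

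**Weight of one subject-period.** In the balanced 2x2 design the treatment estimate is half the difference between sequences in mean within-subject contrast. One subject's value in one period has weight ½ × 1/30 = 1/60. An error of the full effect in that value shifts the estimate by 5.5/60 = 0.09 mmHg.

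**Gap (a).** Assume a true off-drug effect of zero and an imputed value carrying the full on-drug effect. Each affected lorundrostat period then adds 0.09 mmHg; three would add 3 × 5.5/60 = 0.28 mmHg. Both the count of three and the full on-drug value are assumptions. Since the sequence distribution is not restricted to on-drug subjects, 0.09 is a ceiling per subject under them.

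**Gap (b).** If a fraction q of PL subjects is never dosed in Period 2 and has no lorundrostat effect there, the expected estimate is 5.5 × (1 − q/2).
- q = 5%: 5.5 × 0.975 = 5.36 mmHg.
- q = 10%: 5.5 × 0.95 = 5.23 mmHg.

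A simulated within-subject contrast adjusted for the baseline difference (correlation 0.55) agreed: 5.49 with no such subject, 5.42 with one of 30, 5.23 with three and 4.94 with six.

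Power under the present rule is Φ(diluted effect/2.05 − 1.645). For comparison, k such subjects are dropped from the contrast, assuming non-informative stopping. The effect stays 5.5 and the standard error is multiplied by √[(1/30 + 1/(30 − k))/(2/30)].

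| k of 30 | Effect, present rule | Power, present rule | Power, subjects dropped |
|---|---|---|---|
| 1 | 5.41 | 0.839 | 0.845 |
| 3 | 5.23 | 0.817 | 0.833 |
| 6 | 4.95 | 0.779 | 0.811 |

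At k = 3 the rule itself costs 0.833 − 0.817 = 1.6 percentage points. The rest of the fall from 85% comes from losing the subjects' information.

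**The case against.** Analysis by assignment is a stated choice. The FAS goes by assignment, Table 4 defines treatment through the randomized sequence, and keeping observed post-stop values under the assigned label is what treatment policy means. Gap (b) biases towards no effect, so it cannot create a false superiority claim. All of this stands, and it is why the primary rule should remain.

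A reader might infer that undosed Period 2 values should be set to missing and imputed under MAR from dosed subjects. The documents do not support that as the primary rule. Table 6 treats missingness after ICE 1 as MNAR, so on-drug values would replace real readings after adverse-event stops. Applied to every undosed Period 2, it would also discard valid off-drug readings of lorundrostat-first (LP) subjects, which serve properly as placebo data.

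On gap (a), stoppers are asked to attend all visits, so it needs a non-AE stop and a missing value together. The planned observed-data-only sensitivity analysis (SAP 6.4.1.5) removes the imputation altogether. Both points limit the size. They do not explain why the primary analysis should treat equally off-drug subjects differently, and the all-MAR sensitivity analysis extends the favourable imputation instead of testing it.

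The disposition and exposure summaries (SAP 6.3.1, 6.3.4) will show doses and stops by period. That makes the cases visible but does not say how the efficacy analysis handles them. No legible sensitivity analysis isolates gap (b), because those values are observed.

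**Conclusion.** The point holds as two modest gaps in one definition. Gap (a) is an inconsistency with the plan's own treatment-policy strategy and can favour lorundrostat, by at most about 0.09 mmHg per affected lorundrostat period under the assumptions shown. Gap (b) dilutes the effect by about 0.09 mmHg per affected PL subject: 5.5 falls to about 5.36-5.23 mmHg if 5-10% of the PL sequence is affected. Against an implied standard error of 2.05 mmHg, both are small unless several subjects are involved.

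Three limits apply. The documents give no discontinuation rate, so every frequency is an assumption. No sentence says that a permanent stop in Period 1 rules out Period 2 dosing; this is inferred from permanent discontinuation of a study drug that covers both products. And Table 5 is silent on period; it does not say that the event is defined per subject.

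A reader might also conclude that the two gaps cancel, or that the primary result is inflated overall. Neither follows: the directions are opposite, and the frequencies are separate and unknown.

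**What to change.** 1. In Tables 5 and 6, extend ICE 1 to permanent discontinuation of investigational drug for any reason in Protocol 7.1. Observed values are still used; missing ones are imputed under the ICE 1 row. Cost: wording, a slightly more conservative estimate, and reliance on what may be a small pool of retrieved dropouts, with the existing jump-to-reference fallback.

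2. Record ICE 1 by treatment period and state that treatment policy by assignment remains the primary rule, including for a Period 2 that was never dosed. Amend the rationale so that it covers that case.

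3. Add one sensitivity analysis in which Period 2 of PL subjects with no Period 2 dose is not counted as lorundrostat. Leave LP subjects' observed off-drug Period 2 values in as placebo. Cost: one further model run, which rests on those stops being non-informative.

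Do not make MAR imputation of observed values the primary rule. None of these changes affects dosing, visits or clinical management.
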